7.2.4 Modification of CVC effect by Sex and Race

Analyses 1b above will be repeated replacing statin-use with a) sex assigned at birth b) race (Black versus non-black).

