10.3 Randomization and Stratification

At study entry, participants will be randomized at a 2:1 ratio (CVC arm: placebo arm), using permuted blocks stratified by statin use. Institutional balance will not be used at randomization.

While enrollment is ongoing, enrollment limits will be increased to replace participants who are randomized but do not start treatment.

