10.6 Analyses

All statistical tests will be two-sided with a nominal alpha level of 0.05. No adjustment for multiple testing will be performed. Stratification will be taken into account in all analyses unless stated otherwise.

Since the goal of the study is to determine the biological activity of CVC on vascular inflammation, the primary analytic approach will be per protocol and limited to participants who remain on study treatment without change in background ART drug class per the study design.

Baseline is defined as pre-entry for TBR and SUV, average of entry and pre-entry for immunology markers, and entry for all other outcome measures.

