2.4 Overview of Sample Size Considerations

The target sample size is 75 participants (50 in the CVC arm and 25 in the placebo arm) with baseline and follow-up PET/CT. To allow for some loss to follow-up and participants unwilling or unable to complete 2 scans, the study planned to enroll 93 participants (62 in the CVC arm and 31 in the placebo arm). Final enrollment was 110 participants.

The primary analysis will focus on between-treatment arm differences in the within-participant changes in arterial MDS TBR (the measure of arterial inflammation by PET/CT). Based on a superiority trial design with two-sided $\alpha=0.05$, assuming a standard deviation (SD) of 0.065 \log_{10} TBR for change in MDS TBR, a total of 75 participants providing complete, evaluable data sets will ensure 80% power to detect a between-groups difference of 0.046 \log_{10} MDS TBR (which is a 10% reduction from baseline).

The assumptions underlying the power calculation are as follows:

- 1) The target effect size for the change in MDS TBR on therapy of 10% is based on the observation of a statin intensification study.
- 2) The assumed SD for change in (\log_{10}) MDS TBR of 0.065 is derived from the placebo arm of ACTG A5314.

3) The use of a two-sided, two-sample T-test with type-I error rate of 5%.

The assumption that 93 enrolled participants will provide 75 participants with evaluable data is derived by 20% total data loss due to drop-out after randomization (including premature discontinuation of study treatment and change in background ART drug class).

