4.2 Analysis Approaches

- Descriptive summaries in Section 5 will be presented for both the Safety set and Efficacy set, unless otherwise specified.
- Summary statistics for discrete and continuous outcomes will be detailed under each report-content in Sections 5 - 9.
- All statistical tests will be two-sided with a nominal alpha level of 0.05.
 - No adjustment for multiple testing will be performed.
- Stratification will be taken into account in efficacy outcome analyses unless stated otherwise.
- No statistical comparisons across groups for baseline characteristics are planned.
- Missing data for TBR analyses will be handled using multiple imputation; sensitivity analyses will be complete case where missing data are ignored.
- Missing data for biomarker analyses will be ignored (i.e., all analyses will be complete case).

Report Contents

5 Participant Characteristics and Disposition

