7.2.3 Regression Analysis of Difference in Change in TBR between Treatment Arms

- Analysis set(s):
 1. Outcome: Efficacy set
 2. (Primary only) Sensitivity analysis: Complete-case set
 3. (Primary only) Supplementary analysis 1: Supplementary set 1
 4. (Primary only) Supplementary analysis 2: Supplementary set 2

- Analysis method:
 - Linear regression of change in TBR on treatment arm, adjusted by statin-use.
 - Linear regression above with interaction between treatment arm and statin-use.

NOTE: Linear regression with interaction (b) for secondary outcomes will be done only if linear regression with interaction of primary outcome shows that change in MDS TBR is different by statin-use.

Table	Regression Analysis Results		
Outcome	Characteristic	Summary Statistic(s)	Statistical Test
PRIMARY	Change in Index vessel MDS TBR (a)	Treatment parameter estimate	95% confidence interval, p-value
	Change in Index vessel MDS TBR given statin-use (b)	Treatment parameter estimate	95% confidence interval, p-value of interaction effect of statin-use
	Change in Index vessel MDS TBR given no statin-use (b)	Treatment parameter estimate	
Outcome	Characteristic	Summary Statistic(s)	Statistical Test
Secondary	Change in aortic vessel TBR (a)	Treatment parameter estimate	95% confidence interval, p-value
	Change in bilateral carotid vessel TBR (a)	Treatment parameter estimate	95% confidence interval, p-value

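### As written, the SAP's sex and race effect-modification models leave out statin use, the only randomization stratum; keep it in, and add a companion model with arm-by-statin

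*SAP*

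**What the plan says.** SAP 7.2.3 defines two models for the between-arm comparison. Model (a) is "Linear regression of change in TBR on treatment arm, adjusted by statin-use". Model (b) is "Linear regression above with interaction between treatment arm and statin-use". SAP 7.2.4 then turns to sex and race: "Analyses 1b above will be repeated replacing statin-use with a) sex assigned at birth b) race (Black versus non-black").

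Protocol 10.3 randomizes 2:1 "using permuted blocks stratified by statin use", and names no other factor. The default for analysis appears twice. SAP 4.2 says "Stratification will be taken into account in efficacy outcome analyses unless stated otherwise", and Protocol 10.6 says "Stratification will be taken into account in all analyses unless stated otherwise". SAP 7.2.4 gives no reason for departing from that default, and no other section puts statin use back into the sex and race models.

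**The concern.** If statin use is replaced, model (b) becomes change on arm, sex and arm-by-sex, and likewise for race. Two terms go: the statin main effect, which represents the stratified design, and arm-by-statin, the one interaction that the SAP tests immediately before.

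The first loss is a departure from the plan's own rule. The second affects interpretation. Randomization balances the arms within statin strata; it does not balance statin use between women and men or between racial groups. If CVC acts differently in statin users, and statin use differs between the subgroups, part of a reported sex or race difference would reflect statin use. SAP 7.4 and Section 8 send the SUV and biomarker outcomes through the Section 7.2 analyses, so the same wording may carry over to them.

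**Working it through.** **1. The plan's own figure.** The documents give no operating characteristics for the sex and race models. The nearest stated figure is "80% power to detect a between-groups difference of 0.046" log10 TBR, with 50 and 25 evaluable participants, SD 0.065 and two-sided alpha 0.05 (SAP 2.4).
- SE = 0.065 × √(1/50 + 1/25) = 0.0159, and 0.046/0.0159 = 2.89.
- Normal approximation: Φ(2.89 - 1.96) = 82.4%. Noncentral t: 81.4%.

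The stated 80% reproduces, so SD 0.065 is used below. The sample size is not in question.

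**2. Inputs.**
- From the documents: SD 0.065, 2:1 allocation within statin strata, alpha 0.05 two-sided, final enrollment 110, data loss 20%. Evaluable N = 110 × 0.80 = 88.
- Assumed, because the documents do not give them: 25% female; statin use 30% in women and 60% in men; a statin-by-CVC difference of 0 to 0.08 log10; no sex difference in the CVC effect once statin use is allowed for.

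**3. Expected distortion.** With arm-by-statin left out, the expected arm-by-sex coefficient is

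(statin-by-CVC difference) × (gap in statin prevalence between the groups).

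- At 0.046: 0.046 × 0.30 = 0.014 log10.
- At 0.08: 0.08 × 0.30 = 0.024 log10.
- If either factor is zero: 0.

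For scale, 22 women and 66 men split 2:1 give an interaction SE of 0.065 × √(1/14.67 + 1/7.33 + 1/44 + 1/22) = 0.034 log10. Simulation gives 0.035. Both distortions are smaller than one SE.

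**4. Simulated rejection rates for arm-by-sex.** There were 3,000 to 4,000 trials per scenario; ranges span repeated runs.

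| Statin-by-CVC difference | Prevalence gap | As written | Plus statin main effect | Plus statin and arm-by-statin |
|---|---|---|---|---|
| 0.02-0.03 | 30 points | 4.8-5.2% | | |
| 0.046 | 30 points | 6.0-6.3% | | |
| 0.08 | 30 points | 7.6-8.2% | 10.4-10.6% | 4.9-5.5% |
| 0.046-0.08 | 10 points | 3.5-5.3% | | |

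Blank cells were not tabulated. With a difference of 0.06 and a statin main effect of 0.03, runs of the written model gave 5.1% to 7.8%; the relative direction of the two effects matters.

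A deliberately extreme case has N = 75, subgroups of equal size, statin use 70% against 30%, and a difference of 0.092, twice the target effect. The distortion is then 0.092 × 0.40 = 0.037. Rejection is 16% as written, 21% with the statin main effect only, and about 5% with both statin terms.

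**5. Precision.**
- Adding the statin main effect multiplies the interaction SE by 1.006 when statin use does not predict change, and by 0.944 when its main effect is 0.05 log10. That is +1% to -6%.
- Adding arm-by-statin as well, when no such interaction exists, moves the SE from 0.0350 to 0.0369. 0.0369/0.0350 = 1.05, or about +5%.

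**The case against.** Four points can be made for the plan.

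- **The question may be marginal.** SAP 7.2.4 asks whether the CVC effect differs between the sexes or racial groups, not why. In the simulated setting with a difference of 0.08, the average CVC effect really does differ by sex, by 0.024 log10, and the written model estimates that without bias. Its rejections are false only for a question conditional on statin use. This stands, and is the reason for putting arm-by-statin in a companion model rather than in the main one.
- **The stratum may be meant to stay.** Model (b) builds on a model already adjusted for statin use, and the default rules could be read as keeping that adjustment while only the interacting factor is swapped. This is possible. But the wording replaces statin use without qualification, so it needs clarifying either way. On this reading arm-by-statin is still absent.
- **Misattribution needs two conditions together,** and the documents support neither: they give no statin use by sex or race, and no statin-by-CVC difference. This stands.
- **The precision gain is slight.** This also stands: at best 6%.

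A reader might infer that the written models will produce spurious sex or race findings, or that the stratified design is wasted. The documents do not support either. The first needs a large assumed interaction joined to a large assumed gap. As for the second, stratification serves the primary comparison, and model (a) keeps statin use there.

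**Conclusion.** The wording departs from the plan's default without a stated reason, and should be corrected. The statistical cost of leaving it is modest: an interaction SE that could be up to about 6% smaller, and, under the assumed 30-point gap with 25% women, a rejection rate of about 5-6% for a statin-by-CVC difference up to the full 0.046 target and about 8% at 0.08. These rates refer to a null of no sex difference conditional on statin use. The 16% figure belongs only to the extreme scenario.

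It would be wrong to conclude that restoring the statin main effect cures misattribution. In the 0.08 scenario it raised rejection from about 8% to over 10%. Only a model that also contains arm-by-statin addresses that question.

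The written model remains a valid estimate of the marginal subgroup difference. The primary model, alpha and sample size are unaffected. This is a free improvement of low priority.

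**What to change.** In SAP 7.2.4, reword the replacement so that, for sex and race separately:

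1. The main model regresses change on arm, statin use, subgroup and arm-by-subgroup.
2. A companion model adds arm-by-statin and is reported beside it, to show whether a sex or race difference persists once a statin-by-CVC difference is allowed for.

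Apply the same wording wherever SAP 7.4 and Section 8 carry these models over to other outcomes.

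The cost is one sentence and no new data. The main model uses one more degree of freedom than the written one, and the companion uses two. The companion's interaction SE is about 5% larger when there is no statin interaction, which is why it should sit beside the main model and not replace it.

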7.3 Correlates of MDS TBR of the Index Vessel

These analyses are planned for the Final Report.

- Analysis set(s): Efficacy set
- Outcomes: 1) Baseline MDS TBR of the index vessel 2) Change in MDS TBR of the index vessel
- Covariates: Age, sex, race, BMI, use of statins at entry, ART (INSTI vs NNRTI), perceived stress scale, diet, average CVC trough (analysis of change only)

With the exception of average CVC trough, all measures are at entry. In the event of a positive effect of CVC, analyses of change will be limited to participants in the CVC arm.
- Analysis method:
 - Descriptive graphic displays of the distribution TBR by each of the covariates of interest
 - Linear regression of TBR adjusted for each covariate in turn (i.e., unadjusted analyses).

Analyses of change in MDS TBR will also adjust for baseline MDS TBR.
 - Linear regression of TBR adjusted for each covariate with evidence of association with TBR in unadjusted analyses. Given the relatively small sample size, evidence of association will be judged with either relaxed type 1 error or clinically meaningful effect sizes.
- Presentation of results: Forest plot for each outcome showing parameter estimates and 95% confidence interval.

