- History of hypertension or blood pressure $\geq 130/80 \text{ mmHg}$ measured during screening
NOTE: See the A5415 Manual of Procedures (MOPS) for **blood pressure measurement guidance**.
- Elevated LDL cholesterol (fasting LDL of $>160 \text{ mg/dL}$; result from sample taken within 90 days prior to study entry can be used)
- Low HDL cholesterol ($<40 \text{ mg/dL}$; result from sample taken within 90 days prior to study entry can be used)
- Smoking (any current tobacco smoking)
- Family history of premature CAD (first degree relative with CAD prior to age 55 for male relative and 65 for female relative; participant report is acceptable)
- hsCRP $>2.0 \text{ mg/L}$ within 90 days prior to study entry without an active infection or acute illness at the time the sample was obtained

4.1.7 The following laboratory values obtained within 90 days prior to study entry by any US laboratory that has a CLIA certification or its equivalent, or at any network-approved non-US laboratory that operates in accordance with Good Clinical Laboratory Practices (GCLP) and participates in appropriate external quality assurance programs.

- Absolute neutrophil count (ANC) $>750/\text{mm}^3$
- Platelet count $>100,000/\text{mm}^3$
- Aspartate aminotransferase (AST) (SGOT) $\leq 5x$ upper limit of normal (ULN)
- Alanine aminotransferase (ALT) (SGPT) $\leq 5x$ ULN
- Alkaline phosphatase $\leq 5x$ ULN
- Estimated glomerular filtration rate (GFR) $\geq 60 \text{ mL/min}/1.73 \text{ m}^2$ as calculated using the Chronic Kidney Disease Epidemiology Collaboration (CKD-Epi) equation

NOTE: See the A5415 MOPS for further information and a link to the CKD-Epi equation and calculator.

4.1.8 Pre-entry FDG-PET/CT imaging (within 60 days prior to study entry) that has been deemed:

- Interpretable as assessed by the central imaging core laboratory
AND
- Without incidental findings that will preclude participation in the study at the discretion of the site investigator

4.1.9 No plans to receive immunizations 7 days prior to the week 24 study visit.

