2.1 Study Design

A5415 is a double-blind, randomized, placebo-controlled, phase II trial to evaluate 24 weeks of Cenicriviroc mesylate (CVC) to reduce arterial inflammation among individuals living with chronic HIV on ART with viral suppression. CVC or placebo for CVC will be administered for 24 weeks to participants. The target sample size was 93 participants (62 in the CVC arm and 31 in the placebo arm). The study enrolled between May 2023 and January 2024 with a final sample size of 110 participants.

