4.1.2 Participant Exclusions

Participants who had any events below will be excluded from efficacy data to be analyzed, per handling of intercurrent events (Section 2.3.1):

- Never started treatment
- Deemed clinically ineligible for the study
- Took prohibited medication(s) during the study
- Died
- Became pregnant

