4.1.4 Analysis Sets

Efficacy set (per-protocol set): All eligible participants who remain on study treatment for at least 22 weeks and remain on the same ART drug class during their entire study period.

Complete-case set: Efficacy set participants who have baseline-week 24 pair of PET/CT scan data.

Supplementary efficacy set one: All eligible participants in the efficacy set as well as participants who remained on study treatment for at least 12 weeks and remained on the same ART drug class during their entire study period.

Supplementary efficacy set two: All eligible participants in the efficacy set excluding participants with confirmed HIV-1 RNA > 200 copies/mL or ≥ 14 consecutive days of ART interruption at any time during the course of the study.

Safety set: All enrolled participants who initiate study treatment.

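### SAP 7.3 limits the correlates analysis of baseline MDS TBR to the Efficacy set, so usable pre-entry scans are left out for no stated reason

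*SAP*

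**What the plan says.** SAP 7.3 plans regressions of index-vessel MDS TBR on age, sex, race, BMI, statin use, ART class, perceived stress and diet. Average CVC trough is added for change only. The outcomes line reads "Outcomes: 1) Baseline MDS TBR of the index vessel 2) Change in MDS TBR of the index vessel", and a single line covers both: "Analysis set(s): Efficacy set". On timing, the section states "With the exception of average CVC trough, all measures are at entry".

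SAP 4.1.4 defines the Efficacy set as "All eligible participants who remain on study treatment for at least 22 weeks and remain on the same ART drug class" throughout the study. SAP 4.1.2 adds "Participants who had any events below will be excluded from efficacy data to be analyzed" and lists never starting treatment, being found clinically ineligible, prohibited medication, death and pregnancy.

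Protocol 4.1.8 requires, before entry, a scan that is "Interpretable as assessed by the central imaging core laboratory". SAP 3.1 fixes both the most diseased segment and the index vessel from the baseline scan. SAP 2.1 reports that the study closed "with a final sample size of 110 participants".

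**The concern.** Outcome 1 is a cross-sectional association observed before any study drug is taken. It uses no treatment, follow-up or week 24 data, yet a participant enters the analysis only after meeting conditions that are settled up to 22 weeks or more later.

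Two things are at stake. The first is precision, because scans that were acquired and centrally accepted are not used. SAP 7.3 itself calls the sample relatively small and proposes a relaxed type 1 error for selecting covariates; using the available scans would be a better first remedy. The second is interpretation, because the result describes people who stayed on treatment and not those who were enrolled.

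The stated reason for per-protocol analysis (Protocol 2.1 and 10.6) is to measure the biological activity of CVC. That reason does not extend to an association that predates treatment.

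**Working it through.** **Is any post-baseline information needed for outcome 1?**

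- Outcome: segment and index vessel are both set at baseline (SAP 3.1).
- Covariates: at entry by SAP 7.3. The stress scale is scheduled around the pre-entry scan (Protocol 6.3.13), and the first food diary is collected at entry (Protocol 6.1).
- Records: forms are completed through the Entry visit even for participants who never start treatment (Protocol 6.2.4).

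So no post-baseline information is needed.

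**Does another planned table fill the gap?** No. The TBR summaries in SAP 7.2.1 also use the Efficacy set. The baseline tables in SAP 5.5 cover the Safety set but do not list TBR.

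**The plan's own loss figures** (Protocol 10.4)

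- 93 enrolled, 20% total loss: 93 × 0.80 = 74.4, against 75 stated. Read the other way, 1 − 75/93 = 19.4%. The figure reproduces.
- The same section uses 15% for non-imaging outcomes, because losses from scan scheduling and quality do not apply there. The difference, 20% − 15% = 5 points, is therefore imaging loss.
- Missed or unreadable week 24 scans are multiply imputed (SAP 7.2) and do not remove anyone from the Efficacy set; SAP 4.1.4 has a separate Complete-case set for paired scans. So 15% is the closer planning figure for exclusion from the Efficacy set, and 20% is an upper one.

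**Cost in precision.** The actual loss d is not given, so it is assumed. With N = 110:

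- analysed = N(1 − d); left out = N·d
- standard-error ratio = √[N / N(1 − d)] = 1/√(1 − d), taking the residual SD and covariate spread as equal in both sets
- smallest correlation detectable with 80% power at two-sided 0.05 = tanh[(1.960 + 0.842)/√(n − 3)], where n is the number analysed

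| Assumed loss d | Analysed | Left out | SE ratio | Detectable correlation |
|---|---|---|---|---|
| 0 (all 110) | 110 | 0 | 1.000 | 0.264 |
| 10% | 99 | 11 | 1.054 | 0.278 |
| 15% | 93.5 | 16.5 | 1.085 | 0.286 |
| 20% | 88 | 22 | 1.118 | 0.295 |

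The 110 is an upper limit. Anyone found clinically ineligible should leave both sets, and missing stress or diet data would reduce the numbers in the models that use them.

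**Bias.** If retention depends only on covariates in a correctly specified model, the coefficients for those covariates are not biased. Bias needs retention to be related to baseline TBR given the covariates in the model, for example through an omitted predictor of TBR. SAP 7.3 first fits each covariate alone, where an omitted predictor is easier to have. Even so, the discontinuation criteria in Protocol 9.1 and 9.2 do not include a TBR value, and neither document shows a link between retention and baseline TBR.

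**The case against.** The strongest reply is that one analysis set lets the two outcomes be read side by side in the same participants, and the change models adjust for baseline MDS TBR. The analysis is also peripheral: correlates of baseline TBR are not among the objectives or the listed outcome measures, and the work is deferred to the Final Report. The precision cost is modest, with a detectable correlation of 0.264 against 0.278 to 0.295.

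The points about standing and size are correct, and they limit the weight of this concern. Comparability is weaker as a defence. The SAP does not give it as a reason, and an Efficacy-set version of outcome 1 can still be shown. SAP 7.3 would itself limit the change analyses to the CVC arm if CVC shows a positive effect, so the two outcomes would then cover different participants anyway.

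A reader might also infer that a fifth of the data is discarded. The documents do not support that as a fact: the 20% is a planning figure for paired scans, it includes imaging loss that is imputed, and no Efficacy-set count is reported. Nor can it be said that all 110 belong in the analysis, because SAP 4.1.2 provides for enrolled participants later found ineligible.

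**Conclusion.** The point holds as an avoidable loss of information. Outcome 1 in SAP 7.3 is restricted by events after baseline, no reason is stated, and no other planned table covers baseline TBR in a wider set. On an assumed loss of 10% to 20%, about 11 to 22 baseline scans of 110 are unused and standard errors are 5.4% to 11.8% larger. At the protocol's 15%, about 16 or 17 scans are unused and standard errors are 8.5% larger. These sizes rest on planning figures and not on the trial's actual exclusions.

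A reader might go further and call the result selection bias. The documents support only the description that the result applies to participants who stayed on treatment. Dependence of retention on the modelled covariates alone would not bias their coefficients, and a dependence on baseline TBR given those covariates cannot be shown from the documents. The primary comparison and the listed outcomes are untouched.

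**What to change.** In SAP 7.3, give each outcome its own analysis set:

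- Outcome 1 (baseline): all eligible enrolled participants with an interpretable pre-entry scan, leaving out those deemed clinically ineligible.
- Outcome 2 (change): the Efficacy set, as now.
- Optionally, repeat outcome 1 in the Efficacy set as a sensitivity analysis, so that the two outcomes can still be compared in the same participants.

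Report the number analysed for each outcome. The cost is a line or two of SAP wording and, if wanted, one more forest plot. No new data are needed.

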8.1.1 Distribution Plot of Biomarkers by Visit Week

Analysis set(s): Efficacy set

Stratification: Overall, by statin-use

Grouped by: Baseline, Week 24, Change

- Figure: Jitter and boxplot of biomarkers at baseline and week 24 by treatment arms (with a 3rd group of boxplots showing the within-participant change)

9 Pharmacokinetic (PK) / Pharmacodynamic (PD) Outcomes

Analyses in this section are subject to change based on pending review of current literature of CVC and ART drug-drug interactions. Based on review of participant regimens, only bictegravir (BIC), dolutegravir (DTG), rilpivirine (RPV), tenofovir alafenamide (TAF), emtricitabine (FTC), and lamivudine (3TC) have exposure by at least 10 participants.

All PK outcomes are limited to participants in the CVC arm.

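### SAP 7.3 drops the placebo arm from the correlates-of-change analysis after a positive CVC result, so a general predictor of change cannot be told from a modifier of the CVC effect

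*SAP*

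**What the plan says.** SAP 7.3 plans regressions of two outcomes, baseline MDS TBR of the index vessel and its change, in the Efficacy set, which holds both arms. For change it adds a rule that depends on the result: "In the event of a positive effect of CVC, analyses of change will be limited to participants in the CVC arm". It does not say whether a positive effect means a p-value, a direction or a size.

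There are nine covariates: age, sex, race, BMI, statin use, ART class, and then "perceived stress scale, diet, average CVC trough (analysis of change only"). Treatment arm is not among them. Covariates enter one at a time, with baseline MDS TBR added for change. Those with evidence of association then go into a joint model. No arm-by-covariate term is listed.

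Three other places bear on this:

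- SAP 7.2.3(b) fits a treatment-by-statin interaction on the primary outcome, and 7.2.4 repeats it for sex and for race.
- The opening of SAP section 9 states: "All PK outcomes are limited to participants in the CVC arm".
- Protocol 11.3.1 has CVC trough determined only in those randomized to active drug.

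**The concern.** A regression of change on a covariate within the CVC arm estimates one slope. That slope is the sum of two parts: how the covariate relates to change without CVC, and how it alters the effect of CVC. Only the placebo slope separates them. SAP 7.3 discards the placebo arm in exactly the case where readers will most want to know what goes with benefit. Ordinary prognostic factors, or regression effects not fully removed by the baseline term, could then be read from the forest plot as correlates of CVC benefit. A genuine modifier could also be missed if the covariate matters on placebo but not on CVC.

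If the result is not positive, both arms seem to stay in. With no arm term, the pooled slope is a weighted mix of the two arm slopes and again does not separate the parts.

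**Working it through.** **Inputs from the documents (SAP 2.4).** The target is given as "The target sample size is 75 participants (50 in the CVC arm and 25 in the placebo arm"). The SD of change is given as "MDS TBR of 0.065 is derived from the placebo arm of ACTG A5314", on the log10 scale. The planned effect is a "between-groups difference of 0.046" log10. The test is a two-sided two-sample t-test at 5%.

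**The plan's own figure first.** The SAP says "a total of 75 participants providing complete, evaluable data sets will ensure 80% power to detect" that difference.
- SE = 0.065 × √(1/50 + 1/25) = 0.0159.
- 0.046 / 0.0159 = 2.89.
- The noncentral t with 73 df gives 81.4% power, so the stated 80% reproduces. The documents give no power for SAP 7.3.

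**Assumed case for SAP 7.3.** A binary covariate is split 50/50 in each arm. It either shifts change by 0.046 log10 equally in both arms (purely prognostic) or does so in the CVC arm only (a true modifier). The size is borrowed from the planned treatment effect; the documents give no covariate effects.

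**Formulas at 50 + 25.**
- CVC-arm slope: SE = 2 × 0.065 / √50 = 0.0184. Ratio 0.046 / 0.0184 = 2.50, which gives 69% power with 48 df.
- Placebo slope: SE = 2 × 0.065 / √25 = 0.0260.
- Difference of slopes: SE = √(0.0184² + 0.0260²) = 0.0318. Ratio 0.046 / 0.0318 = 1.44, which gives 30% power with 71 df.

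**Simulation (4,000 trials per row, 50 + 25, SD 0.065): share flagged at p < 0.05.**

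| True pattern | CVC arm only | Pooled, no arm term | Arm-by-covariate |
|---|---|---|---|
| No relation | 5% | 5% | 5% |
| 0.046 in both arms (prognostic) | 69% | 84% | 4% |
| 0.046 in CVC arm only (modifier) | 69% | 50% | 29% |
| 0.046 on placebo, 0 on CVC (modifier) | 5% | 10% | 30% |

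In the CVC-only column, rows two and three are the same: that analysis cannot distinguish the two patterns. In row four it sees nothing although the covariate does modify the effect. A continuous covariate with 0.023 per SD in both arms gives 66%, 80% and 5% across the three columns.

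**At the final enrollment.** 110 × 0.80 = 88 evaluable, taken as 59 + 29 (assumed, since actual evaluable numbers are not given). For the prognostic pattern the CVC-only fit flags about 76% and the interaction test about 5%.

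**Does keeping placebo cost precision on the CVC slope?** In a two-arm model with a covariate-by-arm term, the CVC slope has SE 2 × 0.065 / √59 = 0.017, the same as in the CVC-only fit when the residual SD is equal in both arms.

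**The case against.** The strongest reply is that SAP 7.3 is about correlates. It covers baseline TBR as well as change, and it nowhere undertakes to identify CVC responders. Effect modification has its own analyses in 7.2.3(b) and 7.2.4, in both arms with an interaction term. That stands. A reader might infer that the SAP leaves the question of who responds to CVC unaddressed; for statin use, sex and race it does not.

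A second reply is that within-arm analysis of CVC is a declared aim. The Protocol's rationale for 2:1 randomization cites extra power for within-group changes on CVC. This also stands, but the two-arm model still delivers the CVC-arm slope, so nothing is given up.

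Third, the pooled branch without an arm term is inferred from silence, and SAP 1.1 defers table outlines and coding details to an Analysis Implementation Plan that is not available here. That is fair. The explicit part is the dropping of placebo after a positive result.

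A reader might also infer that average CVC trough, set to zero on placebo, would act as a stand-in for arm and create a false exposure association. The documents do not support this. No document proposes that coding, and Protocol 11.3.1 and SAP section 9 both point to trough being analysed in the CVC arm only. SAP 7.3 merely fails to say so.

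Finally, an interaction test has low power here: about 30% for 0.046 at 50 + 25, with about 0.090 log10 (1 − 10^−0.090 = 19%) needed for roughly 80%. That is a reason to report an estimate and interval rather than a verdict by p-value. It is not a reason to prefer a slope that answers a different question.

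**Conclusion.** The point holds in limited form. The rule in SAP 7.3 makes the analysed population depend on an undefined trial result. When the result is positive, it removes the comparison that separates prediction of change from modification of the CVC effect. Under the assumed balanced covariate with equal slopes in both arms, the CVC-only fit flags it in 69% of trials (50 + 25) to 76% (59 + 29), against about 4–5% for the interaction. Covariate prevalence and effect size are assumptions; SD, effect scale and target numbers are the SAP's.

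The gap concerns age, BMI, ART class, perceived stress and diet. The section is exploratory, planned for the Final Report, and has no bearing on the primary test. It would be wrong to read this as a threat to the trial's main conclusion. It is a minor improvement, worth making because it is nearly free.

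**What to change.** Replace the result-dependent sentence in SAP 7.3 with a rule that applies whatever the primary result:

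- Fit change in MDS TBR in both arms with arm, baseline MDS TBR, the covariate and covariate-by-arm.
- Report the slope in each arm and their difference, each with a 95% interval.
- Fit average CVC trough in the CVC arm only, and say that this follows SAP section 9.
- State that a CVC-arm slope alone is not evidence of differential response.

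The cost is a few sentences of SAP text and wider forest plots; no new data are needed. The CVC-arm slope loses no precision. The difference in slopes will be imprecise (SE about 0.032 log10 in the assumed case at 50 + 25), and the text should say so and treat it as an estimate.
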